A9. ClinicalTrials.gov Registration

Does this protocol/trial require registration on ClinicalTrials.gov due to it: meeting the definition of an Applicable Clinical Trial, being required under the terms and conditions of an award, or being proposed to be published in ICMJE journals? Yes

Who will be responsible for registering and maintaining the registration of this Applicable Clinical Trial? The BCM PI will register the trial because either:

- the trial is BCM PI-initiated,
- BCM is the lead site of this multicenter trial, or,
- the industry sponsor has instructed the BCM PI to register the trial, or,
- registration of this trail is required as a term and condition of the reward by the funding agency.

ClinicalTrials.gov Identifier: NCT04307355

Section B: Exempt Request

B. Exempt From IRB Review

Not Applicable

Section C: Background Information

Reduction mammoplasty is a procedure in which a volumetric reduction of the breast is done for cosmetic purposes. This technique includes an infra-mammary perpendicular incision joined by a T-inframammary fold in it; central area, that further continue vertically until surrounding the nipple perimeter.

The likelihood of poor healing outcomes and adverse events (e.g., wound dehiscence, thick scar, itchy or unsortable scars) at the T-inframammary fold (anchor incision) of the breast wound incision is relatively high (estimated to be 10%-15%). This pure outcome is attributed to the corner (as a result of the T-inframammary fold) low blood supply. Given the fact that there are two corners in this particular procedure, the chances of adverse events are higher due to the point of most tension for the entire breast. Continuous oxygen therapy may reduce the likelihood of poor outcomes and adverse events.

In our institution, the Plastic Surgery Department utilizes Dermabond glue (sano acrylic) and Prineotape (air and water sealed) to close the wound around the areola and over the T-inframammary fold. Depending on the incision size, a JP drain could be placed (10% of the cases). Furthermore, the Prineo tape is kept on for a period of 3 weeks. Once it is removed, the incisions are normally healed. However, if wound dehiscence presents, it normally happens between the second and third post-operative week. Then, the Prineo tape has to be removed before the expected time period. Therefore, an external dressing might be able to avoid wound dehiscence during this period.

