Section D: Purpose and Objectives

This is an exploratory randomized controlled trial study to test feasibility, acceptability, and proof of concept efficacy of Continuous Diffusion of Oxygen (CDO) adjunct therapy for decreasing healing time and reducing tissue dehiscence post breast reconstruction. We will assess the benefit of this novel adjunct therapy on successful closure, tissue oxygenation, scar appearance, and patients centered outcomes including perception of benefit, pain, sleep quality, and quality of life. Since all procedures are bilateral, an internal randomization will be performed based on breast side (left or right). The patients will be given CDO in one breast defined as intervention breast. A 5x5 cm CDO dressing will be placed by the plastic surgeon over the T-inframammary fold after the Dermabond glue and Prineo tape are placed. Then, Silagen (a silicon sheet) will be placed on top of the CDO dressing to secure it in place. The remaining parts of the incision will be covered with Dermabond Glue and Prineo tape. On the contrary, the control breast will be given the standard dressing (Dermabond + Prineo tape). The study device OxyGeni is a Class II medical device which has US Food and Drug Administration (FDA) 510(k) clearance, CE-Mark approval and a Health Canada license for the treatment of wounds.

Outcomes will be assessed on weekly-basis up to 4 weeks. Here are the aims and hypotheses for this study:

Aim1: To assess effectiveness of CDO adjunct therapy in reducing the likelihood of wound complication post-surgical

closure.

H1: CDO adjunct therapy will reduce the likelihood of surgical wound complication including dehiscence and its volume, infection or surgical revision, compare to standard of care dressing.

Aim2: To assess changes in skin perfusion in patients treated with CDO adjunct therapy.

H2: CDO adjunct therapy will improve tissue oxygen saturation in >50% of the patients as compared to baseline (measurements at baseline, 2 weeks, and 4 weeks).

Aim3: To evaluate changes in quality of life, anxiety during dressing change, and psychosocial parameters in patients with a surgical wound treated by CDO adjunct therapy

H3: CDO adjunct therapy will improve subject quality of life, reduce anxiety, and reduce perceived pain and physiological stress response during dressing change compared to the control group.

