Visit 5, at minimum 6 months post-op *duration: 50 minutes. This is an optional visit where research staff will take a NIRS image, a Digital Photograph, report adverse events since last visit, and assess patient scar satisfaction using validated questionnaires (PASS and POSAS). Moreover, the plastic surgeon will provide their observation of the scarring using validated questionnaires (SCAR and POSAS). The patient will be seen in the Vascular Clinic (Procedure Room). Female research coordinator will perform all measurements and questionnaires under ethics protocol. Should the patient not be available to attend the clinic in-person, they will have the option to do the questionnaires remotely and upload digital photos of the area via RedCAP. This study visit is added to provide long-term information regarding scarring and effect of study device on long-term healing outcomes.

The research coordinator will make sure at all times that patient does not experience discomfort and all ethical protocols will be followed.

Section G: Sample Size/Data Analysis

G1. Sample Size

How many subjects (or specimens, or charts) will be used in this study? Local: 30 Worldwide: 30

Please indicate why you chose the sample size proposed:

This is an exploratory proof of concept study. The anticipated sample size (n=30) is selected based on resource/budget availability and feasibility to be completed within one year. This sample size is estimated to be sufficient to determine feasibility and proof of concept efficacy of Continuous Diffusion of Oxygen (CDO) adjunct therapy to improve tissue oxygen supply and reduce likelihood of adverse events. Upon initial results and availability of budget, the sample size may be increased to clinically validate the initial observation. In this case, an addendum will be submitted to increase sample size if needed.

G2. Data Analysis

Provide a description of your plan for data analysis. State the types of comparisons you plan (e.g. comparison of means, comparison of proportions, regressions, analysis of variance). Which is the PRIMARY comparison/analysis? How will the analyses proposed relate to the primary purposes of your study?

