The primary outcomes of this study are 1) tissue oxygen saturation level measured using Kent Imaging system and 2) incident of wound related adverse events (e.g., incident wound dehiscence, infection, scar size, and surgical revision). Secondarily outcomes include pain, wound outcomes (e.g. wound size, scar size, wound healing rate, etc assessed using digital photography), area of inflammation (assessed using KENT), and pain (assessed using VAS). Exploratory outcomes include patient quality of life, sleep quality, anxiety, and depression. Baseline between group comparison will be dine using two-sample t-tests, Mann-Whitney U-test, or Chi-square depend on scale/distribution of the variables (i.e., parametric, non-parametric, or binary). We will use general mixed linear model and post-hoc analysis to examine difference between

groups (time, group, and time X group effect) for skin perfusion. We will adjust the results based on baseline incision wound size and duration between baseline and last visit assessment. Subjects with at least one week continue treatment will be included in the analysis. Controlled variables include age, BMI, baseline vascular health. We will use chi-square to estimate whether the number of wound complication incidents is less in the intervention group compared to the control group. Chi-square or repeated ANOVA or Mann-U test depend on scale/distribution of the variable will be used for secondary and exploratory outcomes.

Section H: Potential Risks/Discomforts

H1. Potential Risks/Discomforts

Describe and assess any potential risks/discomforts; (physical, psychological, social, legal, or other) and assess the likelihood and seriousness of such risks:

As any new investigational device, there are some risks, which are anticipated to be minimal in this study. Some of potential risks could be: * Skin related discomfort, erythema (redness), skin rash, dryness and itching. * Skin allergic reaction to dressing adhesive. * Tenderness/minor ache around the dressing application area * Heat sensation and/or perspiration with wearing dressing * Some impairment of mobility due to dressing unit

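### The wound-complication primary outcome gets only an ordinary chi-square: no effect size or interval, no account of the left/right pairing, and too few expected events for the approximation

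*Combined protocol and SAP*

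**What the plan says.** Section D sets up a within-patient comparison: "Since all procedures are bilateral, an internal randomization will be performed based on breast side (left or right"). One breast receives CDO and the other the standard dressing. Follow-up is weekly: "Outcomes will be assessed on weekly-basis up to 4 weeks".

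G2 lists two primary outcomes, tissue oxygen saturation and "incident of wound related adverse events (e.g., incident wound dehiscence, infection, scar size, and surgical revision"). For skin perfusion it plans a mixed linear model with time, group and interaction effects. For complications its whole plan is: "We will use chi-square to estimate whether the number of wound complication incidents is less in the intervention group", compared with the control group. The documents name no risk difference, ratio, odds ratio or confidence interval for this outcome, and no paired method.

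G1 explains the size of the trial: "The anticipated sample size (n=30) is selected based on resource/budget availability and feasibility to be completed within one year". It states no alpha, power or target effect, but asserts: "This sample size is estimated to be sufficient to determine feasibility and proof of concept efficacy". It adds: "Upon initial results and availability of budget, the sample size may be increased to clinically validate the initial observation". Section C gives the only event rate; it says that the likelihood of poor healing at the T-fold "is relatively high (estimated to be 10%-15" per cent).

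**The concern.** G2 asks a test to do the work of an estimate. There are three defects.

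- **No estimate.** A chi-square statistic does not measure how much lower the complication rate is, or how uncertain that is. A proof-of-concept trial needs to pass both on to whatever follows.
- **Pairing ignored.** An ordinary two-group chi-square compares 30 breasts with 30 breasts as if they came from 60 people. The evidence about CDO lies in the patients whose two breasts differ, and the chi-square table does not show how many there are.
- **Sparse data.** With a handful of events the chi-square approximation is poor, and the p-value depends heavily on which variant is run. G2 does not say whether a continuity correction applies.

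At stake is the reading of a primary outcome. The same few events can fall on either side of 0.05 depending on an unstated choice of test, with no planned estimate to anchor the interpretation.

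**Working it through.** G1 gives no statistical derivation of n = 30, so there is no planned figure to reproduce.

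**Inputs.** 30 patients, hence 30 CDO and 30 control breasts (G1, Section D). Background rate 10% to 15% (Section C). Assumptions: the rate is per breast, all 30 patients are analysed, and 0.05 two-sided is the reference level.

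**Expected events.** Control side: 30 × 0.10 = 3.0 and 30 × 0.15 = 4.5. The expected event cell per side is 3.0 to 4.5 if CDO has no effect. If CDO halves the rate it is (3.0 + 1.5)/2 = 2.25 to (4.5 + 2.25)/2 = 3.4. All are below the customary minimum of 5.

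**Formulas.** Let c be the number of patients with an event on the control side only, and b the number with an event on the CDO side only.

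- Uncorrected chi-square for x control and y CDO events: 60 × [x(30 − y) − y(30 − x)]² / [30 × 30 × (x + y) × (60 − x − y)].
- Exact McNemar: two-sided binomial test of b out of b + c with probability 0.5.
- Estimate, CDO minus control: d = (b − c)/30. The paired score (Tango) 95% interval is the set of d for which |b − c − 30d| / √{30[2q + d(1 − d)]} ≤ 1.96, where q is the constrained maximum-likelihood probability of a control-only pair.

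**Worked case, 4 v 0.** Chi-square = 60 × (4 × 30 − 0)² / (900 × 4 × 56) = 864,000/201,600 = 4.29, p = 0.038. Exact McNemar p = 2 × 0.5⁴ = 0.125. Fisher p = 0.112.

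Results when no patient has events in both breasts (negative differences favour CDO):

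| Control v CDO | Chi-square p | Fisher p | Exact McNemar p | Difference, points | Paired score 95% CI |
|---|---|---|---|---|---|
| 4 v 0 | 0.038 | 0.112 | 0.125 | −13.3 | −29.7 to −0.5 |
| 3 v 0 | 0.076 | 0.237 | 0.250 | −10.0 | −25.6 to +2.5 |
| 3 v 1 | 0.301 | 0.612 | 0.625 | −6.7 | −23.1 to +8.7 |
| 4 v 2 | 0.389 | 0.671 | 0.688 | −6.7 | −24.8 to +11.1 |

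**Effect of ignoring pairing.** Keep the discordant pairs at 4 v 0 and add one patient with events in both breasts, so that the totals become 5 v 1. Chi-square = 60 × (5 × 29 − 1 × 25)² / (900 × 6 × 54) = 864,000/291,600 = 2.96, p = 0.085. The estimate, the paired interval and McNemar's p are unchanged, because that patient does not distinguish the two sides.

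**What the test can show.** If CDO halves the rate, the exact chance of a significant result favouring CDO is 10.3% (10% v 5%) or 15.5% (15% v 7.5%) with the uncorrected chi-square. With exact McNemar, assuming no within-patient correlation, it is 2.0% or 5.6%. A non-significant result is therefore likely even with a useful effect.

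**The case against.** The strongest reply is that this is a declared pilot, that G2 answers an institutional form asking for types of comparison, and that anyone running a chi-square has the event counts and can report proportions and direction. Part of this stands. Low power is not a fault in a pilot, and the counts do show direction. But counts per side do not give a paired interval, which needs the discordant pairs, and G2 commits to neither.

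A second reply concerns the 4 v 0 example. The recommended interval there (−29.7 to −0.5) also just excludes zero, so it sides with the chi-square rather than with McNemar. That is correct. The example does not show that the chi-square verdict is false; it shows that the verdict depends on the test chosen. Nor should a reader infer that the chi-square produces many false positives. With independent breasts and no effect, it favours CDO in about 2.7% (10% rate) or 2.6% (15% rate) of trials, close to the nominal 2.5%, and exact McNemar is conservative.

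Three other stronger readings are tempting and unsupported:

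- **That the p-value drives a decision to enlarge the trial.** G1 mentions initial results and budget. It names no p-value, threshold or other criterion, and initial results could include oxygenation and feasibility.
- **That no primary outcome has a between-breast estimate.** The mixed model for perfusion yields one. Only the commitment to report it with an interval is missing.
- **That a non-significant result will be reported as no difference.** The documents do not say so.

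**Conclusion.** The point holds for the complication outcome. Its only planned analysis gives no effect size or interval, does not respect the within-patient randomisation, and rests on a large-sample approximation with about 3 to 4.5 expected control-side events. The consequence is material: identical discordant data (4 v 0) give p = 0.038, 0.085 or 0.125 according to the test used and whether a patient with events in both breasts happens to be present.

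The event count is derived, not stated in the plan. Section C does not say whether its rate is per breast or per patient. The G2 outcome is wider than T-fold healing, which could raise the count; the rule requiring at least one week of treatment could lower it. The defects of estimation and pairing do not depend on the count. This should be corrected before analysis, but it does not undermine the design.

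**What to change.** In G2, replace the chi-square sentence for complications with the following commitments:

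1. Each breast is classified once, as having or not having at least one complication by week 4, because G2 now refers to a number of incidents and a breast could have several.
2. The main result is the within-patient difference in the proportion of breasts with a complication (CDO minus control), with a paired score 95% interval and the counts of patients with events on both sides, CDO only, control only and neither.
3. Exact McNemar is reported as a supportive p-value. If it and the interval disagree, as at 4 v 0, the interval governs.
4. A non-significant test will not be read as evidence of no effect.

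For oxygen saturation, add only that the mixed-model between-breast difference will be reported with its 95% interval.

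The cost is a few sentences, with no new data or procedures. The downside is that the reported conclusion will look less certain. The change does not supply a criterion for enlarging the trial; if one is wanted, G1 would have to state it.

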1) Baseline (Surgery Day, Week 0) 2) Visit 1 (Week 1 Post-Op) 3) Visit 2 (Week 2 Post-Op) 4) Visit 3 (Week 3 Post-Op) 5) Visit 4 (Week 4 Post-Op) 6) Visit 5 (minimum of 6 months Post-Op) *optional

Baseline: Subjects will be randomized to internal control. Since all procedures are bilateral, an internal randomization will be performed based on breast side (left or right). The patients will be given CDO in one breast defined as intervention breast. A 5x5 cm CDO dressing will be placed by the plastic surgeon over the T-inframammary fold after the Dermabond glue and Prineo tape are placed. Then, Silagen (a silicon sheet) will be placed on top of the CDO dressing to secure it in place. The remaining parts of the incision will be covered with Dermabond Glue and Prineo tape. On the contrary, the control breast will be given the standard dressing (Dermabond + Prineo tape).

Visits 1-4: All patients will have baseline assessment including visual, dermal, and tissue oxygen saturation level. The status of wound closure and presence of wound complication will be monitored every week. Each subjects will need up to 5 visits including baseline assessment, and weekly assessment up to 4 weeks or full wound healing or surgical revision, whichever comes first. At each visit, patients will be provided standard of care treatment including regular wound dressing change. Table 1 in attachments' section summarizes the key measurement at each study visit. At Visit 4, the CDO therapy will be removed. Subjects will then have the option to return at minimum 6 months later for a final follow-up visit listed below.

Visits 5: Optional follow-up visits. This visit can also be done remotely should the person not be available to attend the clinic.

Inclusion Criteria:

18-85 years of age. Ability to provide informed consent. Presence of a wound due to surgical intervention and closure. Subject or responsible caregiver is willing and able to maintain the required Continuous Diffusion of Oxygen (CDO) system (if assigned to the intervention group) and applicable dressing changes

Exclusion Criteria:

Active Drug/alcohol abuse (or history of drug/alcohol abuse in last 1 month); excessive lymphedema; presence of active infection; subject has a history of or any intercurrent illnesses or conditions that would compromise the safety of the subject according to judgement of a qualified wound specialist.

F2. Procedure

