Please note that subjects will be consented before performing any study related measurements. This study will not bring any direct costs to the subject. The subject's medical insurance will be billed for all standard of care procedures.

Eligible subjects will be internally randomized and will receive the intervention for 4 weeks. Each subjects will receive standard of care for wound treatment. Intervention side will receive adjunct Continuous Diffusion of Oxygen (CDO) therapy using a novel dressing, which facilitates continuous supply of oxygen to the wound inside the wound dressing using a portable device named OxyGeni . We will collect patient demographics (e.g., age, sex, height, weight, race, ethnicity, marital status, level of education, etc), relevant medical history (e.g., comorbidity, type of surgery, number of prescription and over counter medication, etc), and relevant social factors (e.g., marital status, years of education, type of work, tobacco history, etc) at baseline. Primary outcomes include tissue oxygenation (assessed using Kent Imaging system) and incidence of wound complications (e.g. dehiscence, infection, and surgical revision). Primary outcomes will be assessed at baseline and on a weekly basis for up to 4 weeks. Secondary and exploratory outcomes include inflammation (assessed using a KENT camera), pain (assessed visual analog scale). The secondary and exploratory outcomes will be assessed at baseline and week-4. Other optional assessments include quality of life (NIH Global Health PROMIS), depression (Center for Epidemiologic Studies Depression Scale, CES-D), cognitive function MoCA), and psychosocial metrics (e.g. fatigue, anxiety, frailty, sleep, etc). These assessments are optional and will be done upon time availability and patient acceptance. We anticipate that duration of all assessments will not exceed 60 minutes. We will be reviewing the billing records for our

patients to explore costs of both groups. We may visit the patient's home for an appointment that doesn't require the physician present or to fix any issues with the device.

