Wound Assessment (primary outcome): A digital photo/video of wound will be taken for wound size verification, estimation of wound size, success of wound healing, and determination of wound dehiscence. Measurement will be performed at every visit.

Pain Intensity Assessment (VAS) (secondary outcome): The subject will be provided with a numeric pain scale where he/she will report pain intensity. Research staff will document subject's pain level. (Collected at every visit)

Adverse Event Reporting: Research Staff will document and report any study/non study related incident as per institution regulations. (Collected at baseline and visits 1-4)

Device Acceptability Questionnaire: To determine patient perception of benefit, perceived ease of use, and attitude toward the use of device, we will use a technology acceptance model (TAM) questionnaire tailored for the purpose of this study. This assessment will be done at the conclusion of the study (week-4)

Questionnaires (optional): Quality of Life (PROMIS), functional status, Frailty Status (TSFI), Cognitive Assessment, and Sleep Quality (PSQI). To evaluate functional status, we will use well accepted and validated general functional assessment instruments. PFIBS for Pain Frequency, Intensity and Burden Scale, MOCA for Mental Exam, and Visual analog scale for pain. (All questionnaires are optional and may be done at any study visit upon time availability and patient acceptability). We will add the already approved questionnaires for the parent study, which include pain. Additionally, we will include Likert Scales (Moon SH et al, 2011; Singer AJ et al 1997; Hollander JE et al 1995; and Ridway DM et al 2007) and Patient Attitude to Scarring Scale (PASS, Kantor J et al 2016) and Patient and Observer Scar Assessment Scale (POSAS) to assess the following patient-reported outcomes: patient satisfaction and cosmetic appearance to evaluate scar itchy, perception of scar thickness, scar discomfort, and pain for each wound side (i.e., left and right breast). SCAR may be used to assess plastic surgeon satisfaction with the scarring. These questionnaires will be answered to the best of the participant's abilities. Should the participant lack certain capacities that make it difficult for them to respond to these questionnaires, they will not be conducted with that participant.

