Visit 2, 2 Weeks Post-Op *duration: 50 minutes. Research staff will perform tasks as described above: Pain Questionnaire, NIRS Imaging, Digital Photograph, Adverse Event Reporting, Wound Monitoring, Wound Assessment, Dressing Change and Device Education. The patient will be seen in Vascular Clinic (Procedure Room) for CDO dressing replacement and wound assessment. Female research coordinator will perform all measurements and questionnaires under ethics protocol.

Visit 3, 3 Weeks Post-Op *duration: 50 minutes. Research staff will perform tasks as described above: Pain Questionnaire, Near-Infrared Spectroscopy Imaging, Digital Photograph, Adverse Event Reporting, Wound Monitoring, Wound Assessment, Dressing Change and Device Education. The patient will be seen in Vascular Clinic (Procedure Room) for CDO dressing replacement and wound assessment. Female research coordinator will perform all measurements and questionnaires under ethics protocol.

Visit 4, 4 Weeks Post-Op *duration: 50 minutes. Research staff will perform tasks as described above: Pain Questionnaire, NIRS Imaging, Digital Photograph, Adverse Event Reporting, Wound Monitoring, Wound Assessment, Dressing Change and Device Education. The patient will be seen in Vascular Clinic (Procedure Room) for wound assessment. Female research coordinator will perform all measurements and questionnaires under ethics protocol. This will conclude study and dressing will be removed and device will be collected. Optional questionnaire at this visit include the PASS (Patient Attitude Scarring Scale) and POSAS (Patient and Observer Scar Assessment Scale) which will assess patient attitude and satisfaction with scarring. POSAS and SCAR Scale will also be optional assessments for the plastic surgeon to assess their satisfaction with the scarring.

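### Repeated ANOVA for continuous secondary outcomes drops patients with a missing visit by default; the mixed model already planned for perfusion should be extended to them

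*Combined protocol and SAP*

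**What the plan says.** All references are to the combined protocol and SAP.

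- **Method.** Section G2 specifies a mixed model with time, group and their interaction, for skin perfusion. For everything below the primary outcomes it says: "Chi-square or repeated ANOVA or Mann-U test depend on scale/distribution of the variable will be used for secondary and exploratory outcomes". It gives no method for missing visits.
- **Who is analysed.** G2 includes subjects with at least one week of treatment, and adjusts for the time from baseline to the last visit.
- **When assessment ends.** F1 (Visits 1-4) says "Each subjects will need up to 5 visits including baseline assessment" and then "weekly assessment up to 4 weeks or full wound healing or surgical revision, whichever comes first". Section C says of the closure tape, which stays on for three weeks: "Once it is removed, the incisions are normally healed". F2, in contrast, says "Eligible subjects will be internally randomized and will receive the intervention for 4 weeks", and its Visit 4 entry ends: "This will conclude study and dressing will be removed and device will be collected". Neither F2 statement makes an exception for early healing.
- **When secondary outcomes are measured.** F2 says "The secondary and exploratory outcomes will be assessed at baseline and week-4". Its data-collection list says of pain: "Research staff will document subject's pain level. (Collected at every visit". The same list puts wound photographs at every visit.

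**The concern.** Chi-square and Mann-Whitney tests compare one value per unit. For a continuous secondary outcome followed over visits, such as pain, wound size or inflammation area, repeated ANOVA is therefore the only listed method that uses the repeated measurements. In its classical form it needs every scheduled value, and standard software removes a patient who lacks one. A patient treated for one, two or three weeks qualifies under G2's inclusion rule and would then fall out of the analysis.

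Ordinary missed visits would cost precision in a trial of 30. If assessment also stops at healing or revision, the missing values are tied to the outcome itself. The retained patients would then not represent those randomised, and mean levels and time courses would be distorted.

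**Working it through.** **1. The plan's own figure.** There is nothing to reproduce. G1 sets n = 30 on budget and feasibility, with no error rate, power, effect size, SD or dropout. All rates below are assumptions.

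**2. Ordinary missed visits, everyone followed to week 4.** Assume baseline is complete and each later visit is missed independently with probability m. Complete patients = 30 × (1 − m)^k, where k is the number of post-baseline visits needed.

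| Schedule | k | m = 5% | m = 10% |
|---|---|---|---|
| Every visit (pain, wound photographs) | 4 | 30 × 0.95^4 = 24.4 | 30 × 0.90^4 = 19.7 |
| Baseline and week 4 only | 1 | 30 × 0.95 = 28.5 | 30 × 0.90 = 27.0 |

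For an outcome measured per breast, the smallest paired standardised difference detectable (noncentral t, assumed two-sided 5% level, 80% power) is 0.53 with 30 patients, 0.60 with 24 and 0.66 with 20.

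**3. If the F1 stopping rule operates.** Complete patients = 30 × (1 − h) × (1 − r), where h is the share healed by week 3 and r the share of the rest who are revised. The documents give neither. With r = 0:

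| h | Complete patients | Detectable paired difference |
|---|---|---|
| 20% | 24 | 0.60 |
| 40% | 18 | 0.70 |
| 60% | 12 | 0.89 |
| 80% | 6 | 1.43 |
| 90% | 3 | 3.26 |

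With r = 15% the counts fall to about 20, 15, 10, 5 and 3. The range is too wide to support any single figure.

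**4. What selection does to the between-breast difference.** Paired breasts were simulated with weekly severity scores, and the patient stopped when scores fell below a healing threshold (three thresholds tried; revision not modelled). The full-data week-4 difference was about −1.60. Complete-case results were:

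| Effect | Stop when both breasts healed | Stop when either healed |
|---|---|---|
| Constant | −1.71 to −1.83 | −1.27 to −1.40 |
| Larger in fast healers | −0.51 to −1.09 | −0.29 to +0.26 |

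Under a constant effect the error is 7% to 15% too large (0.11/1.60; 0.24/1.59) or 13% to 21% too small (0.21/1.61; 0.33/1.60). Under a varying effect most of the difference can vanish. Levels shift in every case: at the middle threshold the complete-case control mean at week 4 was 4.0 to 5.1, against about 2.0 in all patients.

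**5. Mixed model on all available visits, middle threshold.** Estimates against full data, by stopping rule: constant effect, −1.59 against −1.60 (both) and −1.54 against −1.57 (either); varying effect, −1.60 against −1.58 (both) and −1.70 against −1.70 (either). This agreement holds only if stopping depends on recorded values.

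**The case against.** The case against has five parts.

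- **G2 offers three tests and never states that incomplete patients are deleted.** True. Skewed outcomes may go to Mann-Whitney, and the one-week rule and the adjustment for time to last visit suggest that incomplete follow-up was meant to be analysed. But G2 does not say how repeated ANOVA would do this, and its default is deletion.
- **The stopping rule may not operate.** F2 describes four weeks and a full Visit 4, and the Section L payment of $450 equals six visits at $75, that is, baseline and five later visits. This stands: the documents conflict, so outcome-driven loss is conditional.
- **The loss cannot be sized.** A reader might take the 10%-15% in Section C as the share of breasts unhealed at week 3 and infer that only about 6 to 8 of 30 patients reach week 4: 30 × (1 − 0.90²) = 5.7 and 30 × (1 − 0.85²) = 8.3, with breasts independent. The documents do not support this. That figure is a rate of poor outcomes including thick or itchy scars, with no week-3 time point.
- **Those left are not simply the slow healers.** A reader might infer this, but F1 also ends assessment at revision, which removes some of the worst courses.
- **A mixed model does not recover everyone.** A reader might infer that it would use all 30. G2 requires a week of treatment, and if an outcome is taken only at baseline and week 4, a patient without week 4 adds almost nothing to the treatment-by-week contrast.

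**Conclusion.** The point holds in a limited form. G2 leaves repeated ANOVA as the only listed method for repeated continuous secondary outcomes, and its default handling of missing visits contradicts G2's inclusion rule. With full follow-up and the assumed 5%-10% of visits missed, the loss is about 6 to 10 of 30 patients for weekly outcomes and 1.5 to 3 for outcomes taken at baseline and week 4. Selection on outcome arises in addition only if the F1 stopping rule is applied, and its extent cannot be calculated from the documents. Because both breasts leave together when a patient stops, the between-breast difference suffers modestly under a constant effect. Large bias needs an effect that varies with healing speed, which the documents neither state nor exclude. The matter concerns secondary and exploratory outcomes of a pilot, but it is cheap to correct before analysis.

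**What to change.** In G2, replace repeated ANOVA for continuous secondary outcomes with the linear mixed model already planned for perfusion, using every available visit:

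- **Outcomes measured per breast:** visit week, treatment and treatment by week, with random effects for patient and for breast within patient.
- **Outcomes scored once per patient**, as F2 describes the pain scale: visit week with a patient random effect only. A single score cannot carry a breast-level treatment term.

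State the missing-at-random assumption. Reconcile F1 with F2 on whether assessments continue to week 4 after healing, and state whether healing means one breast or both. Reconcile the two F2 statements on when secondary outcomes are measured, since the gain from the model depends on the weekly values.

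The cost is a few sentences, with no new data or software. There are two downsides: the result relies on missing at random, and a linear model fits wound size poorly once wounds are closed.
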